5.3.4. Patient Characteristics

Demographic data are collected and reported to demonstrate that the study population represents the target patient population. A summary of baseline participants and disease characteristics, historical diagnoses, pre-existing conditions, and prior therapies will be reported by cohort using descriptive statistics. Other participant baseline characteristics will be summarized by group as deemed appropriate.

5.3.4.1. Demographics

Patient demographics will be summarized as described above. The following demographic information will be included:

- Age
- Gender (male, female)
- Race (American Indian or Alaska Native, Asian, Black or African American, Native Hawaiian or Other Pacific Islander, White, Multiple)
- Region (US, Germany and Poland)
- Country
- Weight (kg)
- Height (cm)
- Body mass index (kg/m²)

A listing of patient demographics will also be provided for the ITT population.

5.3.4.2. Baseline Disease Characteristics

The following baseline disease information (but not limited to only these) will be presented for baseline urticaria clinical characteristics, baseline health outcome measures, and other baseline demographic and disease characteristics as described above:

- Weekly Urticaria Activity Score (UAS7)
- Weekly Itch Severity Score (ISS7)
- Weekly Hives Severity Score (HSS7)
- Dermatology Life Quality Index (DLQI)

5.4. Handling of Dropouts or Missing Data

Missing continuous scores will be imputed using baseline observation carried forward (BOCF) analyses.

The UAS7 score is the sum of the daily UAS scores over 7 days each week. The daily score is the average of 2 results when both entries are made, or it is the single result when only 1 entry is made in a given day. When 1 or more of the daily UAS scores are missing, the following principles will be applied to handle the missing data:

- If a participant has at least 4 nonmissing daily UAS scores within the 7 days prior to the study visit, the UAS7 score is calculated as the sum of the available UAS scores in that week, divided by the number of days that have a nonmissing diary UAS score, multiplied by 7.
- If there are less than 4 nonmissing daily UAS scores within the prior 7 days, then the UAS7 score is missing for the week.

The same principles will be applied to handle the missing data for all of the weekly outcomes.

- Nonresponder imputation (NRI): All participants who discontinue the study or the study treatment at any time for any reason will be defined as nonresponders for the analysis of categorical efficacy variables at discontinuation and subsequent visits.
- Mixed-effects model of repeated measures (MMRM): Continuous variables will be assumed to be missing after discontinuation for which an MMRM analysis will be performed. The model will include treatment, visit, and treatment-by-visit-interaction as fixed categorical effects and baseline and baseline-by-visit-interaction as fixed continuous effects. An unstructured (co)variance structure will be used to model the between- and within-patient errors. If this analysis fails to converge, the heterogeneous autoregressive [ARH(1)], followed by the heterogeneous compound symmetry (CSH), followed by the heterogeneous Toeplitz (TOEPH) will be used. The Kenward-Roger method will be used to estimate the degrees of freedom. Type III tests for the least-squares means (LSM) will be used for the statistical comparison. The LSM difference, standard error, p-value and 100(1-alpha)% CI will also be reported.
- BOCF, as previously stated.

5.5. Efficacy and Health Outcome Analyses

The general methods used to summarize efficacy data, including the definition of baseline value for assessments are described in Section 5.3.

Table FRCF.5.1 Error! Reference source not found.includes the descriptions and derivations of the primary, secondary, and exploratory efficacy and health outcomes.

Table FRCF.5.2 provides the detailed analyses including analysis type, method and imputation, population, time point, and comparisons for efficacy and health outcome analyses.

Page 16

 Table FRCF.5.1.
 Description and Derivation of Primary, Secondary and Exploratory Efficacy Outcomes

Maasura	Description	Variable	Derivation / Comment	Imputation Approach if with Missing Components

		 Time to relapse 	Relapse occurs at the first instance in	Single item, missing if
			Period 3 when a patient's UAS7 score	missing.
			is greater than 6 among the UAS7 \leq 6	
			responders at Week 12.	
Weekly Itch	The ISS7 score is the sum of daily itch	 ISS7 score 	The ISS7 score is the sum of the	When either the morning or
Severity	score (ISS, 0-3 point scale) over 7 days		average daily ISS scores over 7 days	evening score is missing,
Score (ISS7)	(range 0 to 21), with daily itch score: 0		each week (range 0 to 21). The daily	the non-missing ISS score
	= None, 1 $=$ Mild, 2 $=$ Moderate, 3 $=$		ISS score is calculated as the average of	for that day (morning or
	Severe. The daily itch score is the		the morning and evening ISS scores.	evening) will be used as the
	average of the morning and evening			daily score. When one or
	scores.			more of the daily ISS scores
				are missing, the following
				principles will be applied to
				handle the missing data:
				If a patient has at least 4
				non-missing daily ISS
				scores within the 7 days
				prior to the study visit, the
				ISS7 score is calculated as
				the sum of the available ISS
				scores in that week, divided
				by the number of days that
				have a non-missing diary
				ISS score, multiplied by 7.
				If there are less than 4 non
				missing daily ISS scores
				within the prior 7 days, then
				the ISS7 score is missing
				for the week.
		Change from baseline in	Change from baseline: observed ISS7	Missing if baseline or
		ISS7 score	score – baseline ISS7 score	observed value is missing.

Measure	Description	Variable	Derivation / Comment	Imputation Approach if with Missing Components
		ISS7 = 0	Observed ISS7 score = 0 . ISS7 = 0 means complete itch response.	Single item, missing if missing.
Weekly Hives Severity Score (HSS7)	The HSS7 score is the sum of daily number of hives score (HSS, 0–3 point scale) over 7 days (range 0 to 21), with daily number of hives score: 0 = None, 1 = Mild (1-6 hives/12 hour), 2 = Moderate (7-12 hives/12 hour), 3 = Intense (> 12 hives/12 hour). The daily number of hives score is the average of the morning and evening scores.	HSS7 score	The HSS7 score is the sum of the average daily HSS scores over 7 days each week (range 0 to 21). The daily HSS score is calculated as the average of the morning and evening HSS scores.	When either the morning or evening score is missing, the non-missing HSS score for that day (morning or evening) will be used as the daily score. When one or more of the daily HSS scores are missing, the following principles will be applied to handle the missing data: If a patient has at least 4 non-missing daily HSS scores within the 7 days prior to the study visit, the HSS7 score is calculated as the sum of the available HSS scores in that week, divided by the number of days that have a non- missing daily HSS score, multiplied by 7. If there are less than 4 non missing daily HSS scores within the prior 7 days, then the HSS7 score is missing for the week.
		Change from baseline in HSS7 score	Change from baseline: observed HSS7 score – baseline HSS7 score	Missing if baseline or observed value is missing.

Measure	Description	Variable	Derivation / Comment	Imputation Approach if with Missing Components
		• HSS7 = 0	Observed HSS7 score = 0. HSS7 = 0 means complete hives response.	Single item, missing if missing.
Dermatology Life Quality	The Dermatology Life Quality Index (DLQI) is a simple,	 Symptoms and feelings domain 	Sum of questions 1 and 2, range 0 to 6.	N/A – partial assessments cannot be saved.
Index (DLQI)	patient-administered, 10-item, validated, quality-of-life questionnaire	 Daily activities domain 	Sum of questions 3 and 4, range 0 to 6.	N/A – partial assessments cannot be saved.
	that covers 6 domains including symptoms and feelings, daily activities,	• Leisure domain	Sum of questions 5 and 6, range 0 to 6.	N/A – partial assessments cannot be saved.
	leisure, work and school, personal relationships, and treatment. The recall period of this scale is over the "last week." Response categories include "a little," "a lot," and "very much," with corresponding scores of 1, 2, and 3, respectively, and "not at all," or	 Work and school domain 	Sum of questions 7 and 7B (if it is answered), range 0 to 3. Responses of "yes" and "no" on Question 7 are given scores of 3 and 0 respectively. If Question 7 is answered "no" then Question 7b is answered with "a lot", "a little", "not at all" getting scores of 2, 1, 0 respectively.	N/A – partial assessments cannot be saved.
	unanswered ("not relevant") responses scored as 0. Scores range from 0-30	 Personal relationships domain 	Sum of questions 8 and 9, range 0 to 6.	N/A – partial assessments cannot be saved.
	with higher scores indicating greater impairment of quality of life. A DLQI	 Treatment domain 	Question 10, range 0 to 3.	N/A – partial assessments cannot be saved.
	total score of 0 to 1 is considered as having no effect on a patient's	 DLQI total score 	DLQI total score: sum of all six DLQI domain scores, range 0 to 30.	N/A – partial assessments cannot be saved.
	health-related QoL (Hongbo et al. 2005), and a 4-point change from	 Change from baseline in DLQI 	Change from baseline: observed DLQI score – baseline DLQI score	Missing if baseline or observed value is missing.
	baseline is considered as the minimal clinically important difference threshold (Khilji et al. 2002; Basra et al. 2015).	 DLQI 0/1 	Observed DLQI score equals 0 or 1	N/A – partial assessments cannot be saved.

Measure	Variable	Analysis Method	Population (Section 5.3.1)	Comparison/Time Point	Analysis Type
Weekly Urticaria Activity Score	• Change from baseline in UAS7 score at Week 12	ANCOVA using BOCF	mITT; PPS	LY3454738 500-mg vs PBO; Week 12	Primary analysis
(UAS7)	• Percent change from baseline in UAS7 score at Week 12	ANCOVA using BOCF	mITT	LY3454738 500-mg vs PBO; Week 12	Exploratory analysis
	• Change from baseline in UAS7 score by visit (Week 0 through Week 12)	MMRM	mITT	LY3454738 500-mg vs PBO; Week 12	Exploratory analysis
	• Percent change from baseline in UAS7 score by visit (Week 0 through Week 12)	MMRM	mITT	LY3454738 500-mg vs PBO; Week 12	Exploratory analysis
	• Proportion of patients with UAS7 score ≤ 6 at Week 12	Cochran-Mantel-Haenszel test stratified by baseline UAS7 (< median versus ≥ median) using NRI	mITT; PPS	LY3454738 500-mg vs PBO; Week 12	Secondary analysis
	• Proportion of patients with UAS7 score ≤ 6 at Week 12	Cochran-Mantel-Haenszel test stratified by baseline UAS7 (< 28 versus ≥ 28) using NRI	mITT	LY3454738 500-mg vs PBO; Week 12	Exploratory analysis
	• Proportion of patients with UAS7 = 0 at Week 12	Cochran-Mantel-Haenszel test stratified by baseline UAS7 (< median versus ≥ median) using NRI	mITT	LY3454738 500-mg vs PBO; Week 12	Exploratory analysis
	• Proportion of patients with UAS7 = 0 at Week 12	Cochran-Mantel-Haenszel test stratified by baseline UAS7 (< 28 versus ≥ 28) using NRI	mITT	LY3454738 500-mg vs PBO; Week 12	Exploratory analysis

 Table FRCF.5.2.
 Description of Primary, Secondary and Exploratory Efficacy Analyses in Period 2

Measure	Variable	Analysis Method	Population (Section 5.3.1)	Comparison/Time Point	Analysis Type
Weekly Itch Severity Score (ISS7)	• Change from baseline in ISS7 score at Week 12	ANCOVA using BOCF	mITT; PPS	LY3454738 500-mg vs PBO; Week 12	Secondary analysis
	• Percent change from baseline in ISS7 score at Week 12	ANCOVA using BOCF	mITT	LY3454738 500-mg vs PBO; Week 12	Exploratory analysis
	• Change from baseline in ISS7 score by visit (Week 0 through Week 12)	MMRM	mITT	LY3454738 500-mg vs PBO; Week 12	Exploratory analysis
	• Percent change from baseline in ISS7 score by visit (Week 0 through Week 12)	MMRM	mITT	LY3454738 500-mg vs PBO; Week 12	Exploratory analysis
	• Proportion of patients with ISS7 = 0 at Week 12	Cochran-Mantel-Haenszel test stratified by baseline ISS7 (< median versus ≥ median) using NRI	mITT	LY3454738 500-mg vs PBO; Week 12	Exploratory analysis
	• Proportion of patients with ISS7 = 0 at Week 12	Cochran-Mantel-Haenszel test stratified by baseline ISS7 (< 14 versus ≥ 14) using NRI	mITT	LY3454738 500-mg vs PBO; Week 12	Exploratory analysis
Weekly Hives Severity Score	• Change from baseline in HSS7 score at Week 12	ANCOVA using BOCF	mITT; PPS	LY3454738 500-mg vs PBO; Week 12	Secondary analysis
(HSS7)	• Percent change from baseline in HSS7 score at Week 12	ANCOVA using BOCF	mITT	LY3454738 500-mg vs PBO; Week 12	Exploratory analysis
	• Change from baseline in HSS7 score by visit (Week 0 through Week 12)	MMRM	mITT	LY3454738 500-mg vs PBO; Week 12	Exploratory analysis
	• Percent change from baseline in HSS7 score by visit (Week 0 through Week 12)	MMRM	mITT	LY3454738 500-mg vs PBO; Week 12	Exploratory analysis
	• Proportion of patients with HSS7 = 0 at Week 12	Cochran-Mantel-Haenszel test stratified by baseline HSS7 (< median versus ≥ median) using NRI	mITT	LY3454738 500-mg vs PBO; Week 12	Exploratory analysis
	• Proportion of patients with HSS7 = 0 at Week 12	Cochran-Mantel-Haenszel test stratified by baseline HSS7 (< 14 versus ≥ 14) using NRI	mITT	LY3454738 500-mg vs PBO; Week 12	Exploratory analysis

			Population		
			(Section	Comparison/Time	Analysis
Measure	Variable	Analysis Method	5.3.1)	Point	Туре
Dermatology Life	• DLQI total score at Week 12	MMRM	mITT; PPS	LY3454738 500-mg vs	Exploratory
Quality Index	• Change from baseline in DLQI			PBO; Week 12	Analysis
(DLQI)	at Week 12				
	• Proportion of patients with	Logistic regression (Treatment as the	mITT	LY3454738 500-mg vs	Exploratory
	DLQI 0/1 at Week 12	only factor) with NRI		PBO; Week 12	Analysis

Abbreviations: ANCOVA = Analysis of Covariance; BOCF = baseline observation carried forward; mITT = modified intent-to-treat; MMRM = mixed model repeated measures; NRI = nonresponder imputation; PBO = placebo; PPS = per protocol set.

Measure	Variable	Analysis Method	Population (Section 5.3.1)	Analysis Type
Weekly Urticaria Activity Score (UAS7)	• Change from baseline in UAS7 score by visit (Week 12 through Week 24)	Summary Statistics	mITT	Exploratory analysis
	• Proportion of patients with UAS7 score ≤ 6 at Week 24	Summary Statistics	mITT	Exploratory analysis
	• Proportion of patients with UAS7 = 0 at Week 24	Summary Statistics	mITT	Exploratory analysis
	• Proportion of patients who maintain UAS7 score ≤ 6 at Week 24 among the responders at Week 12	Summary Statistics	mITT	Exploratory analysis
	Median time to relapse	Summary Statistics	mITT	Exploratory analysis
Weekly Itch Severity Score (ISS7)	• Change from baseline in ISS7 score by visit (Week 12 through Week 24)	Summary Statistics	mITT	Exploratory analysis
	• Proportion of patients with ISS7 = 0 at Week 24	Summary Statistics	mITT	Exploratory analysis
Weekly Hives Severity Score (HSS7)	• Change from baseline in HSS7 score by visit (Week 12 through Week 24)	Summary Statistics	mITT	Exploratory analysis
	• Proportion of patients with HSS7 = 0 at Week 24	Summary Statistics	mITT	Exploratory analysis

 Table FRCF.5.3.
 Description of Exploratory Efficacy Analyses in Period 3

Abbreviations: mITT = modified intent-to-treat

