Section 5.3.4.2, Baseline Disease Characeteristics	Added this new subsection to clarify the patient's baseline disease activities information we want to collect.	Added more details.
Table FRCF.5.2, Description of Primary, Secondary and Exploratory Efficacy Analyses in Period 2	Added analyses of percent change from baseline for UAS7/ISS7/HSS7 at Week 12. Added analyses on PPS population for some key endpoints. Added the factors in the logistic regression model for DLQI(0,1).	Added more exploratory analyses. Added some analyses on PPS population.
Table FRCF.5.3, Description of Exploratory Efficacy Analyses in Period 3	Changed the analysis method for HSS7 change from baseline from "MMRM" to "Summary Statistics".	Typo correction.
Section 5.7.2, Adverse Events	Clarified the definition for TEAEs.	Minor clarification.

Section # and Name	Description of Change	Brief Rationale
Section 5.7.6.5, Columbia Suicide Severity Rating Scale	Deleted this whole section because this information is not available for this study.	Deleted unnecessary sections.
Section 5.8, Protocol Deviations	Changed the mITT population to PPS population.	Minor clarification.

3. Study Objectives

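### DLQI 0/1 is compared by treatment-only logistic regression: modest power is given up if baseline is prognostic, and nothing is specified for an empty placebo responder cell

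*SAP*

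**What the plan says.** The DLQI 0/1 row of SAP Table FRCF.5.2 gives the method as "Logistic regression (Treatment as the" and continues "only factor) with NRI". The population is mITT, the comparison is LY3454738 500 mg versus placebo at Week 12, and the row is labelled exploratory. The model terms were chosen on purpose: the Amendment A table in the SAP's Revision History records "Added the factors in the logistic regression model for DLQI(0,1").

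Elsewhere the plan uses baseline:

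- SAP 5.3.4.2 lists "Dermatology Life Quality Index (DLQI") among the baseline disease characteristics, and the protocol's schedule of activities collects it at Visit 2.
- Table FRCF.5.1 derives "Change from baseline: observed DLQI score – baseline DLQI score".
- DLQI total score and its change are analysed by MMRM, which under SAP 5.4 includes "baseline and baseline-by-visit-interaction as fixed continuous effects".
- The other binary Period 2 endpoints (UAS7 ≤6, UAS7 = 0, ISS7 = 0, HSS7 = 0) each use a test stratified by their own baseline, for example "Cochran-Mantel-Haenszel test stratified by baseline HSS7 (< median versus ≥ median) using NRI".

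Under the NRI rule in SAP 5.4, "All participants who discontinue the study or the study treatment at any time for any reason will be defined as nonresponders" in the categorical analyses. SAP 5.4 gives a sequence of fallback covariance structures if the MMRM does not converge. It gives no fallback for the logistic model.

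**The concern.** There are two separate issues in one table cell.

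**Baseline.** DLQI 0/1 is an absolute threshold on a 0 to 30 scale, so a participant who starts near it plausibly reaches it more easily than one who starts far above it. If so, a model without baseline DLQI detects a treatment effect less often than one with it. The same instrument is adjusted for baseline in the MMRM row and left unadjusted in the next, with no reason given.

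**Empty cell.** Allocation of 3:1 leaves about 15 placebo participants, and NRI counts every discontinuation as a nonresponse. If no placebo participant responds, the log-odds ratio has no finite maximum-likelihood estimate. Standard output would then show a huge coefficient, a far larger standard error and a Wald p-value near 1, even where the data favour active treatment. With no rule in advance, a replacement method would be chosen after the data are seen.

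**Working it through.** **Inputs.** About 60 participants are randomised 3:1 (SAP 4.1 and 5.2): 60 × 3/4 = 45 active and 60 × 1/4 = 15 placebo. The 52 evaluable participants split 39:13. The documents give no response rate, power or prognostic strength for DLQI 0/1, so all such values below are assumptions.

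**The plan's own figure.** The only stated power is for UAS7 change: about 87% (protocol 9.2), more than 87% (SAP 5.2). With difference 7, SD 7 and 39:13, the noncentrality is 7 / [7 × √(1/39 + 1/13)] = 3.12, and power is Φ(3.12 − 1.96) = 87.7%, or 86.5% by the exact noncentral t. This confirms the 3:1 split but says nothing about DLQI.

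**Probability of no placebo responder.** P = (1 − p)^n, where p is the placebo response rate after NRI.

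| Assumed p | n = 15 (mITT) | n = 13 |
|---|---|---|
| 5% | 46% | 51% |
| 10% | 21% | 25% |
| 15% | 9% | 12% |
| 20% | 3.5% | 5.5% |
| 30% | 0.5% | 1.0% |

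The mITT column is the relevant one, because NRI keeps dropouts in the denominator.

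**What breaks and what does not.** Take an illustrative result of 14/45 active and 0/15 placebo responders.

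- Maximum likelihood: the odds ratio is (14 × 15)/(31 × 0), which is not finite. In a Newton fit the coefficient was 5.4, 10.4 and 22.9 after 5, 10 and 20 iterations. The standard error rose from 5.7 to about 35,000 and the Wald p from 0.35 to 0.9995, without convergence.
- Score test: 60 × (14 × 15)² / (45 × 15 × 14 × 46) = 6.09, p = 0.014.
- Likelihood-ratio test: 9.39, p = 0.002.
- Fisher's exact test: p = 0.013.
- Firth (in a 2×2 table, 0.5 added to each cell): (14.5 × 15.5)/(31.5 × 0.5) = 14.3, log-odds ratio 2.66.
- Maximum likelihood with a baseline covariate added: the treatment coefficient still diverges (22.8, SE about 33,000, at 20 iterations). Baseline adjustment alone does not cure the empty cell.

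**Power from adding baseline.** These are simulations at 45:15 with Firth models and a 5% penalised likelihood-ratio test, assuming placebo log-odds −2.2 at mean baseline and treatment log-odds 1.8. Ranges are across repeated runs; with 1,500 trials the Monte Carlo standard error is about √(0.6 × 0.4/1500) = 1.3 points.

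| Baseline effect (log-odds per SD) | Treatment only | With baseline | Difference within run |
|---|---|---|---|
| 0 | 63% | 62–63% | −1 to 0 |
| 0.7 | 57–60% | 61–62% | 1 to 4 |
| 1.0 | 53–55% | 59–62% | 5 to 7 |

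Type I error was 3–5%. Under a different assumption (placebo −2.4, treatment 2.0; 800 trials), power went from 72% to 72%, 65% to 69% and 55% to 64% at baseline effects of 0, 0.8 and 1.3 per SD. Only that last and strongest effect gives a gain above 7 points.

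**Where the gain comes from.** Adjustment did not shrink the standard error. At 1.0 per SD the mean estimate moved from 1.47 to 1.74 and the mean SE from 0.86 to 0.94, so their ratio rose from 1.71 to 1.85. At 0.7 per SD the estimate moved from 1.61 to 1.75 and the SE from 0.91 to 0.95 (ratio 1.77 to 1.84). The conditional coefficient lies further from zero by more than its standard error grows.

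**The case against.** The case for leaving the row alone is substantial. The endpoint is exploratory and no decision rule depends on it. The terms were specified deliberately, and a sparse model is defensible with about 15 placebo participants. The MMRM already provides a baseline-adjusted comparison on the same instrument. All of this stands, and it is why the point is minor. It does not explain why this binary row alone ignores its baseline, and the MMRM of the total score does not answer the question about the 0/1 threshold.

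A reader might also infer stronger claims that the documents do not support:

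- **That the comparison is biased by baseline imbalance.** Treatment is randomised, so the unadjusted test is valid; its simulated type I error was 3–4%.
- **That omitting baseline loses precision in the usual sense.** In logistic regression the adjusted standard error is larger. What is gained is power, on a conditional rather than a marginal effect.
- **That the analysis fails outright whenever placebo has no responders.** Only the finite estimate and Wald inference fail. The other tests survive if some active participants respond.
- **That a planned odds ratio would be infinite.** The SAP names neither an odds ratio nor a Wald test for this row. The gap is that it names no test or estimate at all.
- **That an empty cell is likely.** That depends on a placebo rate the documents do not give. At 20% or more it is uncommon.

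**Conclusion.** The point holds as a minor improvement. The treatment-only model is valid but inconsistent with the other binary Period 2 rows. At 45:15 it gives up about 0 to 7 points of power for assumed baseline effects up to 1.0 log-odds per SD, with no loss beyond simulation error from adjusting when baseline is not prognostic. The empty-cell gap is separate. It would matter in roughly one trial in five at a 10% placebo rate (21%) and hardly ever at 30% (0.5%). Both sizes rest on assumed response rates and prognostic strength. Neither issue touches the primary conclusion.

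**What to change.** Change the method cell of the DLQI 0/1 row in SAP Table FRCF.5.2 to: *Firth penalised logistic regression with treatment and continuous baseline DLQI, NRI; penalised likelihood-ratio test and odds ratio with profile-likelihood 95% CI.* The two parts do different work: the baseline term recovers power, and the Firth penalty handles the empty cell. Keep the observed proportions by arm as the marginal summary.

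The cost is one table cell and one option in the model statement. The small downside is that the odds ratio becomes conditional on baseline DLQI and should be labelled so. A participant without a baseline DLQI would drop out of the adjusted model, so add a line saying how that case is handled.
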